Research Ethics Committee Protocol Application

Royal Adelaide Hospital

1. Title

Effects of a guar and whey containing preload (Omniblend) on gastric emptying and blood pressure responses to oral glucose in healthy older subjects.

2. Investigator Details and Qualifications

- i. [name], Dip [name], Senior Research Fellow, Adelaide Medical School, University of Adelaide, Adelaide Health and Medical Sciences Building; Ph: [name]; email: [contact]

- ii. [name], MBBS (Hons), FRACP, PhD, MS (Epi), Endocrinologist and Postdoctoral Research Fellow, Royal Adelaide Hospital and University of Adelaide, [name], [contact]

- iii. [name], MBBS, PhD Student, Adelaide Medical School, University of Adelaide, Adelaide Health and Medical Sciences Building; Ph: [name]; email: [contact]

- iv. [name], Honours Student, Adelaide Medical School, University of Adelaide, Adelaide Health and Medical Sciences Building; Ph: [name], email: [contact]

- v. [name], Dip App Sci (Nuclear Medicine), Senior Research Officer, Adelaide Medical School, University of Adelaide, Adelaide Health and Medical Sciences Building; Ph: [name]; email: [contact]

- vi. [name], MD, PhD, Royal Adelaide Hospital Florey Research Fellow, Adelaide Medical School, University of Adelaide, Ph: [name]; email: [contact]

- vii. [name], MBBS, PhD, FRACP, Associate Professor, Adelaide Medical School, University of Adelaide, Royal Adelaide Hospital; Ph: [name]; email: [contact]
- viii. [name], MBBS, PhD, FRACP, Professor of Medicine, Adelaide Medical School, University of Adelaide, Royal Adelaide Hospital; Ph:[name]; email: [contact]

Address for correspondence for Principal Investigator ([name]): University of Adelaide, Adelaide Medical School, University of Adelaide, Adelaide Health and Medical Sciences Building [name].

Abbreviations:

BP = blood pressure; GIP= glucose-dependent insulintropic polypeptide; GLP-1 = glucagon like peptide-1; HR = heart rate; PPH = postprandial hypotension; SMA = superior mesenteric artery; T2DM= type 2 diabetes mellitus

3. Purpose and Aims of the Study

The proposed study is designed to (i) determine the effects of a whey protein/guar preload on gastric emptying and postprandial blood pressure (BP) in response to oral glucose in healthy older subjects and (ii) to determine the relationship between the rate of gastric emptying and the magnitude of the fall in BP following an oral glucose load with and without the preload.

4. Background and Preliminary Studies

Postprandial hypotension (PPH) is now recognised as a frequent and important clinical problem, particularly in the healthy elderly (13 – 38%) [1, 2], and in patients with autonomic dysfunction, often secondary to diabetes (□40%) [1, 3] and Parkinson’s disease (40 – 100%) [1, 3]. The consequences of PPH include syncope and falls [3, 4]. More importantly, PPH is also associated with an increase in mortality [5].

The pathophysiology mediating PPH is complex and yet to be completely understood. However, the interaction between autonomic and neural mechanisms plays an important role in the regulation of postprandial BP, including the release of gastrointestinal hormones, which are influenced by meal composition, extent of gastric distension, and small intestinal nutrient delivery. After a meal, there is an approximate doubling of superior mesenteric artery (SMA) blood flow [3]. In healthy young individuals with intact baroreflex function, the increase in splanchnic blood flow is accompanied by concomitant increases in heart rate (HR), as well as peripheral vascular resistance, stroke volume and cardiac output [6]. In patients with PPH, these compensatory responses are inadequate [3]. We have shown that the postprandial fall in BP is greater when gastric emptying is more rapid in patients with type 2 diabetes (T2DM) [7] as well as in a cohort of 86 healthy older subjects [2].

Current strategies for the management of PPH are limited. We have previously demonstrated that gastric distension attenuates the fall in blood pressure induced by intraduodenal glucose in healthy older subjects. More recently, approaches based on slowing gastric emptying [8, 9] and small intestinal absorption of nutrients [10] have attenuated the magnitude of the fall in postprandial BP.

Guar gum, a gel-forming, unpalatable, and unabsorbable carbohydrate, derived primarily from the ground endosperm of guar beans and used as a bulking agent, attenuated the fall in postprandial BP in healthy older subjects [8] and in patients with T2DM [11] when administered together with a 50-g glucose drink. The effects of guar on BP might be attributed to a number of gastrointestinal mechanisms, including slowing of gastric emptying by increasing the viscosity of the intragastric content, as well as delaying small intestinal nutrient absorption by forming a physical barrier between glucose and small intestinal mucosal cells [8, 11], an hypothesis reinforced by the observation that an intraduodenal infusion of glucose (3 kcal/min) and guar (4g) resulted in a lesser fall in BP and a greater increase in HR in comparison to a glucose infusion alone in healthy older subjects [9]. The potential use of guar in the management of PPH is limited due to its poor palatability and gastrointestinal adverse effects such as diarrhoea, flatulence.

An understanding of the effects of different nutrients on postprandial BP is important in the nutritional management of PPH. For example, a low dose whey protein preload ingested before the meal can slow gastric emptying [12, 13] by stimulating release of glucagon-like peptide-1 (GLP-1) and cholecystokinin patients with T2DM [12].

Omniblend (*Omniblend Innovation*), has recently been developed to control postprandial glycaemia. Omniblend is now available in pharmacies and comprises 5g guar, 20g (whey) protein and 3g lactose (total 80kcal) in a sachet, which is added to a ‘shake and take’ cup containing 150ml water yielding a drink that is available in vanilla, chocolate or ‘savoury’ flavours. In our 12-week double-blind randomised placebo controlled trial, this supplement slowed gastric emptying, attenuated postprandial hyperglycaemia and was well tolerated in subjects with T2DM (n=79) [14].

More recently, our pilot study of 11 healthy older subjects, demonstrated that a preload of Omniblend given 15 min before a 75 g glucose load tends to attenuate the magnitude of the fall in postprandial systolic BP (Figure 1), with a modest lowering in blood glucose and no change in gastric emptying (unpublished data). **The study was generally well tolerated and there were no adverse events.** A limitation of this pilot study is the lack of randomisation of the order of the intervention (this was a pilot added onto a study that was already being performed). Furthermore, gastric emptying was assessed using a breath test technique, an indirect measure of gastric emptying which relies on small intestinal absorption. Given that guar gum affects small intestinal absorption [15], this is not the ideal technique; gastric emptying would preferentially be measured via the ‘gold standard’, scintigraphy.

[figure not shown]

Figure 1: Change in systolic BP from baseline in 11 healthy older subjects following an oral (75g) glucose load with or without an Omniblend preload, administered 15 min before glucose drink (unpublished pilot data).

The primary hypotheses underlying the current study are that (i) a preload of whey protein/guar (Omniblend) will slow gastric emptying in healthy older subjects and (ii) this slowing of gastric emptying will be associated with an attenuation in the fall in BP after oral glucose, and a reduction in splanchnic blood flow. We further hypothesise that the slowing gastric emptying will be associated with a reduction in postprandial hyperglycaemia and glucose absorption will be delayed. The effect of the preload on incretin hormone release (GLP-1 and GIP) is uncertain due to the differing effects of guar and protein on their secretion.

Therefore, the aims of this study are to evaluate the effect of an Omniblend preload on:

- i) BP and HR
- ii) gastric emptying (using scintigraphy) of a 50g glucose load,
- iii) splanchnic blood flow (Doppler ultrasound)
- iv) glucose absorption (utilising 3-OMG) and plasma glucose, serum insulin and

- v) incretin hormones (plasma GLP-1 and GIP).

5. Participants

18 healthy subjects aged 65–80 years will be recruited from existing databases and via advertisements placed around the Adelaide Medical Precinct including the Royal Adelaide Hospital. Sample size requirements have been determined via power calculations $\alpha = 0.05$ and $\beta = 0.8$, performed with systolic BP as the primary outcome parameter, based on our previous data (*unpublished pilot study*). A sample of 18 subjects are required to determine a difference in systolic BP (postprandial AUC) of 3.2mmHg/min.

Subject selection criteria

Inclusion criteria

- Male or female subjects aged 65–80 years
- Body Mass Index 19-30 kg/m²

Exclusion criteria

- History of diabetes mellitus (or fasting plasma glucose ≥ 7.0 mmol/L or HbA1C $\geq 6.5\%$)
- Severe respiratory or cardiovascular disease which would limit tolerance of study
- Hepatic disease as defined by transaminases $> 2 \times$ upper limit of normal or bilirubin $> 2 \times$ upper limit of normal
- Renal disease (creatinine clearance < 50 mL/min)
- Anaemia or iron deficiency

Reference ranges:

Alanine aminotransferase (ALT)	< 55 U/L
Alkaline phosphatase (ALP)	30 - 110 U/L
Aspartate transaminase (AST)	< 45 U/L
Total bilirubin	2 - 24 μ mol/L
Haemoglobin	115 – 165 g/L (Females)
	130 – 180 g/L (Males)

Subjects will undergo concurrent measurements of gastrointestinal (GI) symptoms (questionnaire), gastric emptying (scintigraphy), BP, HR (DINAMAP), SMA blood flow (Doppler ultrasound), blood glucose, serum insulin, plasma GLP-1, GIP and 3-OMG [10, 16] (*Figure 2*).

On arrival, the subject will be seated in front of a gamma camera. A cannula will be inserted into an antecubital vein for blood sampling and an automated BP cuff (DINAMAP ProCare 100, GE Medical Systems, Milwaukee, WI, USA) placed around the opposite arm for BP measurements (systolic, diastolic), and HR [7, 9, 11, 17-24].

After a rest-period of 15-30 minutes to allow baseline BP to settle [10], subjects will be given, in random order, either (i) a test drink containing 50 g glucose labelled with 20 MBq ^{99m}Tc -calcium phytate, made up to 300ml water [16] or (ii) a preload containing 20g whey protein and 5g guar (Omniblend) made up to 150ml with water 15 minutes before the ingestion of the test drink. The preload and test drink will be consumed within 2 minutes. Time zero ($t = 0$) is defined as the time of the end of the test drink ingestion. Dynamic images will be acquired at 1 minute per frame for the first hour and at 3 minutes per frame for another two hours.

BP and HR will be measured at 3 min intervals prior to administration of test drink, and then regularly at 5 min intervals from $t = 5 - 180$ min [7-9, 11, 17-24]. Baseline BP and HR will be calculated as an average of the measurements obtained at $t = -24, -21, -18$ minutes prior to the ingestion of the preload ($t = -15$ minutes), or at $t = -9, -6, -3$ minutes prior to the ingestion of the test drink ($t = 0$ minute) on the study day without a preload.

Venous blood samples (15 mL) will be collected prior to the ingestion of the preload ($t = -18$ minutes) and/or test drink ($t = -2$ minutes) and then at $t = 15, 30, 45, 60, 90, 120, 150, 180$ minutes for measurement of blood glucose, serum insulin, 3-OMG, plasma GLP-1 and GIP. Samples will be stored at -70°C until analysed. Blood glucose concentrations will be immediately determined using a portable blood glucose meter (MediSense Companion 2 meter; MediSense Inc., Waltham, MA, USA) and, plasma glucose, subsequently by YSI to reduce the variability observed with the use of a glucometer [7, 17-19].

Splanchnic blood flow will be assessed by measuring SMA flow with Doppler ultrasound [16]. using a Logiq™9 ultrasound system (GE Healthcare Technologies, Sydney, NSW, Australia). SMA blood flow will be measured immediately prior to administration of the preload (t = -18 min) and/or test drink (t= -2 minutes) and then at t = 15, 30, 45, 60, 90, 120, 150, 180 minutes.

Sensations relating to appetite and PPH symptoms will be evaluated using a visual analogue scale (VAS) immediately prior to the ingestion of the preload (t = -18 minutes) and/or test drink (t= -2 minutes) then at t = 15, 30, 45, 60, 90, 120, 150 and 180 minutes [16].

At t = 180 min, subjects will be offered a light lunch and BP measurements will be taken. They will be permitted to leave when their BP returns to baseline levels.

[figure not shown]

Figure 2: Study design

7. Outcomes

The primary outcomes will be the effects of guar/whey containing preload on gastric emptying, and BP responses to oral glucose as well as the relationships between them in healthy older subjects. Secondary outcomes include effects of guar/whey on: i) SMA blood flow (Doppler ultrasound) ii) postprandial glycaemia (glucose absorption employing 3-OMG, blood glucose and plasma insulin) and iii) incretin effect (GLP-1 and GIP). If the preload attenuates the fall in BP, further evaluation,

Version 2: 1 May 2018

including effects of chronic (~4-8 weeks) administration and in patients with PPH, would be indicated.

8. Ethical Considerations

All aspects of the study will be discussed with each subject during a phone interview and screening visit. An information sheet will be provided, and each participant will be given the opportunity to seek medical advice or to discuss the study with friends or family prior to involvement. Each participant will give written, informed consent, in accordance with the attached form, and the subjects will be free to withdraw from the study at any time. This study will be performed in accordance with the Declaration of Helsinki.

9. Specific Safety Consideration

All techniques are safe and have been extensively employed in published studies conducted by the investigators.

The dose of radiation from each gastric emptying study is within accepted NHMRC guidelines and has been considered acceptable by the Royal Adelaide Hospital Research Ethics Committee (RAH Protocol no.091227B). No women of child-bearing age will be studied with this protocol. Our radiation hot lab, located immediately next door to the Gamma Camera Suite, has been inspected and approved by the Environmental Protection Agency (EPA) as a licenced premise. [name] holds a current radiation licence and is a registered medical radiation practitioner with AHPRA.

Placement of the intravenous cannula may be associated with some minor, and temporary discomfort. Bruising, and in rare and extreme cases, infection, may also occur due to the insertion of the catheter.

In the case that a patient faints while in the Clinical Research Facility, they will be placed in the supine position with legs raised and attended to by a medical member of staff as is our usual practice.

If a medical condition is identified during the course of this study (eg screening examination, blood tests, or during the study days), one of the physicians associated with the study ([name], [name] or [name]) will speak with the subject and liaise with their GP regarding ongoing management/follow up.

The Chairman of the Research Ethics Committee will be notified within 72 hours in the event of a serious adverse event.

10. Drugs

Nil

11. Analysis and Reporting of Results

Data will be analysed using standardised statistical methods (e.g. using repeated measures ANOVA). BP, HR will be assessed as changes from baseline, whereas gastric emptying, SMA blood flow and blood glucose will be analysed as absolute values. The maximum changes from baseline in BP, HR and blood glucose will also be calculated. Areas under the curve (AUCs) will be calculated for BP, HR, SMA blood flow and blood glucose using the trapezoidal rule. Changes in each variable over time will be evaluated with ANOVA. Relationships between variables will be assessed by linear regression analysis. The data will be prepared for publication in a peer-reviewed journal. All records will be kept a minimum of 15 years in the AHMS Building, or a secure offsite storage facility (e.g. Recall) and the study will maintain the anonymity of the participants. No medical records will be required for this project. Only the investigators will have access to the research data and results. The School of Medicine, University of Adelaide, will own all data from this study.

12. References

1. Trahair, L.G., M. Horowitz, and K.L. Jones, *Postprandial Hypotension: A Systematic Review*. Journal of the American Medical Directors Association, 2014. **15**(6): p. 394-409.

2. Trahair, L.G., M. Horowitz, and K.L. Jones, *Postprandial Hypotension Is Associated With More Rapid Gastric Emptying in Healthy Older Individuals*. Journal of the American Medical Directors Association, 2015. **16**(6): p. 521-523.
3. Jansen, R.W. and L.A. Lipsitz, *Postprandial hypotension: epidemiology, pathophysiology, and clinical management*. Ann Intern Med, 1995. **122**(4): p. 286-95.

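### The control day has no wait to match the 15 minutes between preload and glucose, so the blood pressure change from baseline spans 15 more minutes on the preload day; a matched wait and a supportive analysis are a cheap improvement.

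*Protocol*

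**What the plan says.** The study procedures text, which stands before Section 7 of the protocol, fixes the timing.

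- **Rest.** The first drink of the day is given "After a rest-period of 15-30 minutes to allow baseline BP to settle". The same range is stated for both days.
- **Preload.** On one of the two days the preload is given, "made up to 150ml with water 15 minutes before the ingestion of the test drink". No matching interval is described for the other day.
- **Time zero.** On both days it "is defined as the time of the end of the test drink ingestion".
- **Baseline, preload day.** It is "an average of the measurements obtained at $t = -24, -21, -18$ minutes prior to the ingestion of the preload".
- **Baseline, control day.** It is the average of readings at t = -9, -6 and -3 "minutes prior to the ingestion of the test drink ($t = 0$ minute) on the study day without a preload".
- **Reading schedule.** "BP and HR will be measured at 3 min intervals prior to administration of test drink"; the start of these readings is not given.

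Section 11 adds: "BP, HR will be assessed as changes from baseline". The baseline thus enters every change that is analysed, including the maximum change. Section 7 names the BP response to the glucose drink as a primary outcome, next to gastric emptying and the relationship between the two. Section 4 states the aim more broadly, as the effect of the preload on BP and heart rate.

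**The concern.** Both days share the same time zero, but the baseline ends 18 min before it on one day and 3 min before it on the other. The extra 15 min always fall on the preload day, so randomising the order of the days cannot balance them. Two things can happen in that interval: BP can drift with longer sitting, and the preload can act on BP before any glucose is taken. The protocol makes the second plausible. Its background section reports that gastric distension lessens the BP fall after intraduodenal glucose, and that a whey preload releases gut hormones.

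What is at stake is interpretation. Hypothesis (ii) in Section 4 links a smaller BP fall after glucose to slower gastric emptying, and Section 11 plans regressions between variables. A BP difference already present at t = 0 would be counted as part of the response to glucose.

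**Working it through.** **Inputs from the protocol.** Baseline times are -24, -21, -18 min (preload day) and -9, -6, -3 min (control day). The preload is at t = -15, the rest before the first drink is 15-30 min, and readings run to t = 180. The target difference in systolic BP is 3.2 (Section 5), read here as a time-averaged difference in mmHg; that reading is an assumption. The protocol gives no figure for drift or for a pre-glucose preload effect, so there is no stated figure to reproduce.

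**Step 1: where the baselines lie.**
- On the glucose clock, the midpoints are -21 and -6 min, and -6 - (-21) = 15 min apart.
- Relative to the first drink, the preload day gives -21 + 15 = -6 min and the control day -6 min, so there is no difference.

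**Step 2: drift.** Let f(s) be the BP drift after s minutes of rest, and r the length of the rest, taken as equal on both days. Both baselines are at s = r - 9, r - 6 and r - 3, so they cancel. At time t after glucose, the preload day is at s = r + 15 + t and the control day at s = r + t. The difference in change from baseline is

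D(t) = f(r + 15 + t) - f(r + t).

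Assume exponential settling with time constant T. Average D(t) over 0-180 min and divide by the drift between t = -18 and t = 0 on the preload day, f(r + 15) - f(r - 3). The rest length r drops out:

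shift per 1 mmHg = (T/180) × (1 - e^(-15/T)) × (1 - e^(-180/T)) / (e^(3/T) - e^(-15/T)).

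| T (min, assumed) | Calculation | Shift in mean difference (mmHg) | Share of 3.2 |
|---|---|---|---|
| 15 | 0.0833 × 0.6321 × 1.000 / 0.8535 | 0.06 | 2% |
| 30 | 0.1667 × 0.3935 × 0.9975 / 0.4986 | 0.13 | 4% |
| 60 | 0.3333 × 0.2212 × 0.9502 / 0.2725 | 0.26 | 8% |
| 120 | 0.6667 × 0.1175 × 0.7769 / 0.1428 | 0.43 | 13% |
| linear throughout | 15 / 18 | 0.83 | 26% |

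These are averages; under settling, the shift is largest just after t = 0 and then fades.

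**Step 3: the preload's own effect.** If the preload moves BP by b mmHg before glucose and this persists unchanged to 180 min, the mean difference moves by b. If it fades, it moves by less. The ceiling is 1 mmHg per 1 mmHg, or 1/3.2 = 31% of the target. This is an effect of the treatment, not an artefact of timing.

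**Step 4: after the change.** With the same clock on both days, D(t) = f(r + 15 + t) - f(r + 15 + t) = 0, and the drift term vanishes. The preload's pre-glucose effect remains in the total effect. It can be seen separately only from the readings at -9, -6 and -3 min.

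**The case against.** The strongest defence is that each baseline is the last untreated window of its day, taken at the same distance from the first drink after the same stated rest. A pre-preload baseline avoids a baseline measured after the intervention and captures the total effect of preload plus glucose, which is the aim as Section 4 states it. All of this stands. It is why the preload-day baseline should not simply be moved to -9 to -3 min.

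Three stronger readings are tempting, and the protocol does not support them.

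- *The mismatch is a bias fully confounded with treatment.* The preload's own action on BP is part of the treatment effect. Only the drift from 15 more seated minutes is a timing artefact.
- *Every 1 mmHg of drift moves the result by 1 mmHg, so drift of 1 to 3 mmHg would account for 31% to 94% of the target.* That treats drift as a constant offset for three hours. Because the baselines match for rest, settling drift largely cancels (Step 2). Even undiminished linear drift gives 0.83, not 1.
- *With a 15-min rest, the baseline is read only 6 to 12 min after sitting down.* Section 5 seats the subject on arrival, before cannulation and cuff placement, and the rest follows. The readings are 6 to 12 min into the shortest permitted rest, hence longer after sitting, and this applies to both days.

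What the defence does not answer is that no matched interval is described for the control day, and that the primary outcome is worded as the response to glucose. The timeline in Figure 2 could not be seen for this check; if it shows a matched wait, the text should say so.

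**Conclusion.** The point holds as a cheap improvement, not as a flaw that invalidates the primary comparison. The change from baseline spans 15 more minutes on the preload day. The plan is sound for the total effect of preload plus glucose, but it does not separate the preload's pre-glucose effect from the response to glucose.

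The protocol gives neither the size nor the direction of any drift or early preload effect. The drift figures in the working rest on assumed time constants, on equal rest on the two days, and on the 0-180 min mean as the summary. They are shifts per 1 mmHg of drift, not estimates of what will occur. A reader should not infer that the trial will show a false attenuation, or miss a true one, because of this timing.

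**What to change.** - Run the same clock on both days: the same rest, baseline at t = -24, -21 and -18 min, and on the control day a 15-min seated wait from t = -15. Keep this as the primary baseline.
- Report the mean of the t = -9, -6 and -3 min readings on both days. Repeat the BP analysis from it as a supportive analysis, and state that on the preload day this baseline is post-intervention. The 3-min schedule before the test drink already provides these readings; the text should give its start time.
- State that the primary BP analysis estimates the total effect of preload plus glucose, and that the supportive analysis addresses the response to glucose.

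The cost is about 15 min more per subject on the control day and a change of wording. The sample size does not change because of it. Whether the control day should include a control preload drink is a separate question, and this fix does not need one.

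### Systolic BP is analysed as a raw change from a three-reading baseline, and SMA flow and glucose mainly unadjusted; adjusting for the between-day baseline difference would usually be more precise at small cost

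*Protocol*

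**What the plan says.** Section 11 sets the scale for each outcome: "BP, HR will be assessed as changes from baseline, whereas gastric emptying, SMA blood flow and blood glucose will be analysed as absolute values". It offers repeated measures ANOVA as an example of method and names no baseline covariate. It also plans the largest departure from baseline for BP, HR and blood glucose, but not for SMA flow.

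The study procedures text between Sections 5 and 7 defines the BP and HR baseline: "Baseline BP and HR will be calculated as an average of the measurements obtained at" three times. These are t = -24, -21 and -18 min on the preload day and t = -9, -6 and -3 min on the other day. After the drink, BP is read "and then regularly at 5 min intervals from $t = 5 - 180$ min", which is 36 readings. SMA flow has a pre-dose value: "SMA blood flow will be measured immediately prior to administration of the preload (t = -18 min) and/or test drink (t= -2 minutes"). Blood is sampled at the same two pre-dose times.

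The design is within-subject: "subjects will be given, in random order, either (i) a test drink containing 50 g glucose" alone or the same drink after the preload. Section 5 sizes the trial on systolic BP: "A sample of 18 subjects are required to determine a difference in systolic BP (postprandial AUC) of 3.2mmHg/min".

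**The concern.** A change score forces a slope of exactly 1 on the day's baseline. That is the best weight only if a difference in measured baseline between the two days carries over in full to the postprandial level. Three cuff readings are a noisy measure of the day's level. If readings vary independently with equal SD, the sampling variance of the baseline mean is 36/3 = 12 times that of the postprandial mean, and all of it enters the change score.

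Absolute values make the opposite choice, a slope of 0. For SMA flow and glucose, any real between-day difference in starting level then stays in the error term.

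With 18 subjects, and systolic BP AUC as the outcome that sets the sample size, it is worth letting the data choose the weight.

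**Working it through.** **Inputs from the protocol.** N = 18; difference 3.2, stated in mmHg/min for an AUC and read here as a time-averaged difference in mmHg; alpha = 0.05, taken as two-sided; the stated beta of 0.8, read as 80% power; 3 baseline and 36 postprandial readings.

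**Not in the protocol, so assumed.** Let D_post and D_base be a subject's between-day differences in the postprandial and baseline values. Let rho be their correlation (0 to 0.9) and lambda = SD(D_base)/SD(D_post) (0.7 to 1.3).

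**1. The plan's own figure.** N = 18 cannot be reproduced forward, because no SD is given; the calculation is described only as "based on our previous data (*unpublished pilot study"). Solving backward for the SD of the within-subject difference:
- Normal approximation: 3.2 × √18 / (1.960 + 0.842) = 13.58/2.802 = 4.85.
- Noncentral t: 4.57 with 17 df, or 4.55 with 16 df once period is fitted.

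The protocol offers nothing to check these against.

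**2. Large-sample variances, relative to Var(D_post).**
- Absolute values: 1.
- Change score: 1 + lambda² − 2·rho·lambda = (1 − rho²) + (lambda − rho)².
- Baseline-adjusted: 1 − rho².

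In large samples adjustment is therefore never less precise than either planned scale.

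**3. Small-sample cost.** With period fitted, the covariate has 16 residual df. Estimating its slope inflates the variance by 1 + 1/(16 − 2) = 15/14 = 1.07. Error df fall from 16 to 15. If the covariate adds nothing, confidence intervals widen by about 4%.

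**4. BP: adjusted against change score, lambda = 1.** The large-sample ratio is (1 − rho²)/(2 − 2·rho) = (1 + rho)/2. The simulation used n = 18 in two sequences of 9, with period fitted, 40,000 runs per setting, and the change-score analysis set to power 0.80.

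| rho | Large-sample ratio | Simulated ratio | Power, adjusted |
|---|---|---|---|
| 0.2 | 0.60 | 0.64 | 0.94 |
| 0.3 | 0.65 | 0.69 | 0.92 |
| 0.5 | 0.75 | 0.81 | 0.87 |
| 0.7 | 0.85 | 0.91 | 0.83 |
| 0.9 | 0.95 | 1.02 | 0.79 |

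Where the true slope rho/lambda equals 1 (for example rho = lambda = 0.7), adjustment loses: variance × 1.07 and power 0.77. Over the whole assumed grid the ratio runs from 0.39 to 1.07.

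**5. Is a slope below 1 plausible for BP?** Assume a reading SD of 4 to 5, a day-to-day SD of 2 to 5 and a day-specific response SD of 1.5 to 2 mmHg.
- Reading 4, response 2: change-score variance 2 × (16/3 + 16/36 + 4) = 2 × (5.33 + 0.44 + 4) = 19.6, SD 4.4. Baseline noise is 5.33/9.78 = 55% of it.
- Reading 5, response 1.5: 2 × (8.33 + 0.69 + 2.25) = 22.5, SD 4.75. Baseline noise is 74% of it.

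Both SDs lie near the implied 4.57. The best slope is day variance/(day variance + reading variance/3). It runs from 4/(4 + 8.33) = 0.32 to 25/(25 + 5.33) = 0.82. Simulated at n = 18, these assumptions gave variance ratios of 0.54 to 0.97.

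**6. SMA flow and glucose: adjusted against absolute values.** Simulated ratios are 1.07, 1.03, 0.98, 0.81, 0.55 and 0.20 at rho = 0, 0.2, 0.3, 0.5, 0.7 and 0.9. Break-even is where (15/14)(1 − rho²) = 1, so rho² = 1/15 and rho = 0.26, in line with a simulated crossing between about 0.25 and 0.3.

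**The case against.** The strongest reply is that nothing here is an error. Order is randomised, so both planned scales estimate the preload effect without bias. The model is left open, and covariates are commonly left to an analysis plan. Change from baseline also directly expresses the fall in BP that the aims concern.

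Most of this stands, and it limits the point to precision. It does not remove it, because Section 11 does commit to a scale for each outcome. The argument about aims has little force: once the baseline difference is in the model, the treatment estimate is the same whether the response is the postprandial level or its change from baseline.

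Four stronger readings might be inferred, and the documents do not support them:
- *The change-score result would be biased.* It would not be, for the reason above.
- *The trial is underpowered.* No SD is given. The pilot figure in Section 4 shows systolic BP as change from baseline. If the sizing SD came from that scale, the baseline noise is already in the 18, and adjustment is a bonus rather than the repair of a shortfall.
- *Glucose and SMA flow have no use of baseline at all.* Glucose has its planned maximum change. A pre-dose SMA value is measured and could enter the ANOVA as a time point, although that is not the same as adjusting for it.
- *Adjustment is free.* At n = 18 it can lose slightly.

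**Conclusion.** The point holds as a recommendation on efficiency. For BP, a slope of 1 on a three-reading baseline is probably too steep. With lambda = 1 and rho of 0.3 to 0.7, adjustment cuts the variance of the contrast by about 9 to 31% and lifts power from 0.80 to about 0.83 to 0.92. Against that stands a worst case of about 7% more variance and power of 0.77.

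For SMA flow and glucose the support is weaker. There is a gain only if the between-day correlation exceeds about 0.25 to 0.3; at 0.5 the variance falls by about 19%.

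The direction follows from the formulas and the 3-against-36 reading counts. The size rests wholly on assumed correlations and SDs, with 18 completers split evenly between sequences.

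**What to change.** Amend Section 11, before any outcome data are compared by treatment, as follows.

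- **Systolic BP AUC (primary):** regress the within-subject difference in postprandial AUC (preload day minus other day) on the within-subject difference in baseline, plus period. Take the treatment effect at a baseline difference of zero. Use the baselines the protocol already defines: t = -24, -21, -18 min on the preload day and t = -9, -6, -3 min on the other. Working with differences keeps between-subject baseline variation out of the adjustment.
- **HR:** the same model.
- **SMA flow and glucose:** the same model, with the t = -18 min value on the preload day and the pre-drink value on the other. Never use t = -2 min on the preload day: it follows the preload at t = -15 min, is therefore post-treatment, and adjusting for it could bias the effect.
- **Gastric emptying:** no change, as it has no comparable baseline.
- **Display:** keep change from baseline for description.

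The cost is a few lines of wording, one error degree of freedom (16 to 15) and the possible loss of about 7% in variance. No extra measurements or visits are needed.
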